7.5.5.6. Randomisation treatment choice

As part of the six weeks post-intervention visit participants will be asked whether there were any specific reasons which led them to choose their randomisation treatment options.

7.5.5.7. Healthcare Services

Primary and secondary care resource use will be recorded via a patient completed Healthcare Services questionnaire (either on a paper form or electronically) at screening, baseline (if required), six months, 12 months, two and three years after intervention. Participants will be asked to record each visit and the reason for this.

A micro-costing analysis of each intervention will be conducted to inform the within-trial economic evaluation. The resources used for each surgery will be estimated for each trial participant.

Information on the resources needed for each intervention will be derived from data captured in the eCRF and obtained from the trial team.

7.5.5.8. Time and Travel

Information on patient and carer costs will be collected via a Time and Travel questionnaire administered at 12 months post intervention. The questionnaire includes questions relating to travel time, travel costs and time away from usual activities resulting from attendance to healthcare visits. Within this questionnaire, for each of the main types of contact with NHS services, respondents are asked about their method of transport, travel costs, distance travelled, how long it took to get to the venue, what they would have otherwise been doing at this time, whether they were accompanied (and if so, what that person would have otherwise been doing at the time), and how long they spent in total at their appointment.

All the information gathered via the Time and Travel questionnaire will be summarised and categorised by intervention, type of admission and care received. These costs will then be combined with the information gathered via the Health Care Utilisation questionnaires in order to conduct the economic evaluation from a broader, societal perspective.

7.5.5.9. Acceptability Test

Acceptability of the procedure will be assessed after the procedure at the six months timepoint. Patient acceptability to a surgical procedure has no agreed definition [54] but can be defined as "appropriateness in addressing the clinical problem, suitability to individual lifestyle, convenience and effectiveness in managing the clinical problem".[55]

The patient will be asked to answer questions to gauge their feelings of acceptability about their recent surgical procedure using the 'Friends and Family test'; 'Thinking about your procedure overall how was your experience of the procedure?" and 'Please can you tell us why you gave your answer?'

7.5.5.10. Post-Intervention Catheterisation Status

Participants will be asked to answer a question concerning their current catheterisation status at the time of their six months, 12 months, two & three years post-intervention visits. If the participant is currently catheterised when they complete their PROMS at a given post-intervention study visit, then the following questionnaires must not be completed: I-PSS, I-PSS-QOL, ICIQ-MLUTS. The ICIQ-MLUTSsex, ICIQ-LUTSqol, EQ-5D-5L and Healthcare Services questionnaires can still be completed regardless of the participant's catheterisation status.

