3. OBJECTIVES AND OUTCOME MEASURES

	Objectives	Outcome Measures
Primary	To compare the clinical effectiveness of 3 minimally invasive treatments (MITS) to transurethral resection of prostate (TURP) for treatment of bladder outlet obstruction (BOO) due to enlarged prostate over 12 months	Change in international prostate symptom score (I-PSS) from baseline to 12 months post-intervention

Primary Economic	To compare the cost effectiveness of 3 minimally invasive treatments (MITS) to transurethral resection of prostate (TURP) for treatment of bladder outlet obstruction (BOO) due to enlarged prostate	Incremental cost per quality-adjusted life year (QALY) gained at 12 months post-intervention Cost-effectiveness acceptability curves (CEACs) to assess the probability of each of the interventions being considered cost-effective at different willingness-to-pay (WTP) thresholds for a gained QALY QALYs will be calculated using responses to the EQ-5D-5L questionnaire
Secondary	To compare impact on bladder voiding efficiency (BVE) and maximum flow rate (Qmax)	Change from baseline to 12 months post-intervention in: Post void residual Maximum flow rate (Qmax)
	To compare incidence of adverse events	Adverse events up to six months post- intervention collected via: Operative parameters Adverse event review at six weeks and six months post-intervention
	To compare impact on incontinence	International Consultation on Incontinence Questionnaire Male Lower Urinary Tract Symptoms Module (ICIQ-MLUTS) at baseline, six months, 12 months, two and three years post-intervention
	To compare impact on sexual function	ICIQ-MLUTSsex at baseline, six months, 12 months, two and three years post-intervention
	To compare impact on quality of life and general health	I-PSS-QOL at baseline, six months, 12 months, two and three years post- intervention
		 ICIQ-LUTSqol at baseline, six months, 12 months, two and three years post- intervention
		EQ-5D-5L at baseline, six weeks post- intervention, six months, 12 months, two and three months post-intervention
	To establish the most suitable outcome measure for the context of male LUTS intervention	Correlation of I-PSS / ICIQ-MLUTS

	To assess the impact of urinary and sexual symptoms on quality of life	Correlation of overall QOL (ICIQ-LUTSqol) with symptom scores from ICIQ-MLUTSsex and I-PSS questionnaires
	To compare the amount of time spent in hospital post-intervention	Length of post-intervention hospital stay

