elf patient is catheterised at this timepoint then the following PROMS should not be completed; I-PSS, I-PSS-QOL and ICIQ-MLUTS

fScreening PROMS must be completed prior to randomisation. In the event that the time between completing the questionnaires and receiving the intervention is greater than six months, the questionnaires will need to be repeated within three months prior to the procedure.

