10.3. Statistical Analyses

10.3.1. Analysis of the Primary Outcome Measure

Main analysis methods

The main primary objective is to estimate the mean difference in the change in the I-PSS symptom score from baseline to 12 months in men requiring surgery for BOO treated with each MIT compared to TURP assuming all eligible patients would adhere to their randomised treatment allocation.

The main primary estimand is described by the following attributes:

Estimand attribute	Description		
Population	Patients offered surgery for BOO and meeting the PREMISE eligibility		
	criteria		
Treatment conditions	Intervention via PUL, iTIND, Rezum (MITS) vs TURP (Control)		
Outcome measure	Change in I-PSS score from baseline to 12-month follow-up		
Strategies used to handle	Becoming ineligible between randomisation and intervention -		
intercurrent events	principal strata ¹		
	Not undergoing randomised treatment – hypothetical ²		
Population-level summary	Mean difference in I-PSS score at 12 months (adjusted for baseline)		
measure	between each MITS and TURP		

¹The principal strata strategy targets the treatment effect within the subgroup of patients who would not have the intercurrent event, regardless of allocated treatment group

For the pairwise comparison of each MIT to TURP data will be pooled across randomisation schemes as shown in Section 10.2.

If, within each comparison, the proportion of eligible participants not undergoing their allocated treatment is >5% in either randomised treatment group inverse probability weighting (IPW) will be used to estimate the average causal effect of each MIT compared to TURP in the hypothetical setting where all eligible participants adhere to their allocated treatment. This will be implemented in two stages. In the first stage, a logistic regression model will be fitted separately to each randomised treatment group with adherence to assigned treatment as the outcome (dependent variable) and prespecified baseline measures as covariates (to be identified following a review of literature and expert opinion and agreed prior to data lock for the main analysis). The modified ITT population will be used, with all participants continuing to meet the eligibility criteria included. These models will be used to calculate weights (the inverse of participant specific predicted probabilities of adhering to allocated treatment) to be used in the main analysis model (second stage).

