10.3.3. Missing data

Analyses using mixed-effects models will give inference that is valid under a missing at random (MAR) assumption. If there is substantial differential dropout between arms then we will apply sensitivity analyses to explore robustness of results to missing not at random (MNAR) mechanisms.

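### Men catheterised at the 6- or 12-month visit have no I-PSS by rule, and the primary estimand gives no strategy for them, so the non-inferiority test handles them under missing at random

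*Protocol*

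**What the plan says.** - **Outcome.** Section 3 defines the primary outcome as "Change in international prostate symptom score (I-PSS) from baseline to 12 months post-intervention".
- **Rule on the questionnaire.** Section 7.5.5.10 says that for a man catheterised when he completes a visit's questionnaires, "then the following questionnaires must not be completed: I-PSS, I-PSS-QOL, ICIQ-MLUTS". Footnote e to the schedule in 7.12 repeats it: "the following PROMS should not be completed; I-PSS, I-PSS-QOL and ICIQ-MLUTS". The sexual-function, quality-of-life and EQ-5D-5L forms may still be completed.
- **Estimand.** The table in 10.3.1 lists two intercurrent events: "Becoming ineligible between randomisation and intervention" (principal stratum) and "Not undergoing randomised treatment" (hypothetical). Catheterisation after the intervention is not listed.
- **Model.** Section 10.3.1 fits a mixed model to the 6- and 12-month I-PSS in the per-protocol population. Where inverse probability weights are used, they model adherence to the allocated treatment, not whether an I-PSS was obtained.
- **Missing data.** Section 10.3.3 says: "Analyses using mixed-effects models will give inference that is valid under a missing at random (MAR) assumption". It continues: "If there is substantial differential dropout between arms then we will apply sensitivity analyses". It does not define the condition.
- **Catheter data.** Status is recorded at 6 and 12 months and at 2 and 3 years. Catheter use and acute retention are secondary outcomes (section 3) with planned regression analyses (10.3.2).

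**The concern.** Men with a catheter are excluded at entry (6.2), and eligibility is rechecked on the day of the procedure (7.6). In the per-protocol population, a catheter at 6 or 12 months is therefore a state that arose after treatment. It is likely to be related to voiding, which is what the I-PSS measures. Whether the score is missing then depends on the outcome, and missing at random is hard to defend for these men.

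The model in effect gives a catheterised man the score expected of voiding men with similar observed data in his arm. If more men are catheterised at 12 months after one of the minimally invasive treatments than after TURP, part of that treatment's deficit never reaches the comparison, and the result moves towards non-inferiority. The planned safeguard may not start. A man who returns his other questionnaires has arguably not dropped out, and similar totals of missing scores with different causes would not meet a condition based on a difference between arms.

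**Working it through.** **1. Who is affected.** The rule works visit by visit.

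| Catheterised at | 6-month I-PSS | 12-month I-PSS | Position in the model |
|---|---|---|---|
| 6 months only | missing | observed | primary endpoint value present |
| 12 months only | observed | missing | endpoint predicted from his 6-month score and observed men |
| both visits | missing | missing | contributes no outcome |

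Repeating the analysis in the ITT, modified ITT or as-treated population does not recover these scores, because they were never collected.

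**2. The plan's own sample size.** Inputs from 10.2: margin 3, SD 6.3, true difference 0, one-sided alpha 0.0195, power 90%.

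- Normal approximation: n = 2 × 6.3² × (2.064 + 1.282)² / 3² = 98.7, so 99 per arm. The t-based version gives 100 (power 0.9006).
- With 25% attrition: 100 / 0.75 = 133.3, so 134 per arm. Four arms: 4 × 134 = 536.

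The stated figures reproduce and are not in dispute. The SD of 6.3 is stated to come from non-catheterised men.

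**3. Size of the shift.** Shift in the difference = (excess proportion catheterised at 12 months) × (failure score − score implied by the model).

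- *Excess:* the protocol gives no 12-month catheterisation rate for any arm. Values of 1, 3 and 5 percentage points are assumed.
- *Implied score:* 8.5, and *unimproved score:* 20.5. These are the 24-month and baseline I-PSS quoted for iTIND in section 2, used only as an illustration. Gap 12.
- *Worst score:* 35, the top of the scale (7.5.5.1). Gap 35 − 8.5 = 26.5.

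| Assumed excess | Unimproved (× 12) | Share of margin | Scored 35 (× 26.5) | Share of margin |
|---|---|---|---|---|
| 1 point | 0.12 | 4% | 0.27 | 9% |
| 3 points | 0.36 | 12% | 0.80 | 27% |
| 5 points | 0.60 | 20% | 1.33 | 44% |

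A man catheterised at 12 months only, with a poor 6-month score, would be predicted worse than 8.5, so for him the shift is smaller. With equal catheterisation proportions and equal gaps in both arms the shift is zero. With an excess in the TURP arm its sign reverses.

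**4. Power if a failure score entered the primary analysis.** Assume 3% catheterised and 100 per arm, before baseline adjustment. Power = Φ(3 / (SD × √(2/100)) − 2.064).

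- *Scored at baseline* (mean gap 12, SD of 6 assumed among these men): variance = 0.97 × 39.69 + 0.03 × 36 + 0.03 × 0.97 × 144 = 43.77, SD 6.6. Power = Φ(3.206 − 2.064) = 0.87.
- *Scored at 35* (no spread among these men): variance = 0.97 × 39.69 + 0.03 × 0.97 × 26.5² = 58.93, SD 7.7. Power = Φ(2.763 − 2.064) = 0.76.

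**The case against.** - **The catheter data are used.** A reader might infer that the plan ignores them. It does not: catheter use, acute retention and re-intervention have planned comparisons, and a treatment that left more men catheterised should show it there. What stands is that these results do not enter the non-inferiority decision.
- **Not every failure is lost.** A reader might infer that the worst outcomes simply leave the trial. The table in step 1 shows otherwise: only men catheterised at both visits contribute no outcome. Nor do the documents say that every catheter present on a questionnaire day marks failed treatment. Section 7.5.5.12 asks the reason for later episodes, so causes may differ.
- **Direction and size are not documented.** Section 9.3.3 lists urinary retention as expected for all four procedures. The roughly 10% retention and 14.8% failure quoted for iTIND in section 2 might be read as 12-month catheter rates, but they are not. The first is reported alongside complications. The second is failure to improve symptoms at two years, and such men can still be voiding and complete the I-PSS. A definite bias in favour of the minimally invasive treatments cannot be inferred.
- **A composite score is a different estimand.** The 3-point margin is justified as the MCID of the I-PSS, not of a score with imputed failures. This stands against insisting on a composite as the primary analysis.
- **Sensitivity detail belongs in the SAP.** This is often so, and the SAP was not available for this review. But the protocol itself fixes the questionnaire rule, the estimand table, the missing-at-random basis and the condition on the sensitivity analyses. Withholding the form may be sensible, since voiding questions hardly apply to a catheterised man. That makes a stated strategy more necessary.

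**Conclusion.** The concern holds as a gap in the estimand and its sensitivity analyses. Scores are missing by rule for a state likely to be related to the outcome, no strategy is stated for it, and the planned check on missing at random depends on an undefined condition. As written, this missingness could enter the non-inferiority decision unexamined.

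Whether it biases the result, and which way, depends on the 12-month catheterisation proportions by arm, which the protocol does not give. For an assumed excess of 1 to 5 percentage points in a minimally invasive arm, the shift towards non-inferiority is 0.12 to 0.60 points with men scored as unimproved. It is 0.27 to 1.33 points with every such man at the worst possible score. At a 1-point excess it is small; at 5 points it is 20% to 44% of the margin. These figures rest on the borrowed 20.5 and 8.5 and on every such man being predicted at the arm mean.

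**What to change.** 1. In the estimand table of 10.3.1, list catheterisation at the 6- or 12-month assessment as an intercurrent event with a stated strategy. Choose it before anyone involved in the choice sees outcome data by arm.
2. In 10.3.3, remove the condition on differential dropout. For each comparison with TURP, always run (a) a sensitivity analysis scoring catheterised men as failures, at their baseline I-PSS and, as the extreme, at 35; and (b) a delta-adjusted tipping-point analysis.
3. Report the number catheterised at each visit by arm beside the primary result.

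The cost is protocol and SAP wording and some analysis time. Catheter status and baseline I-PSS are already collected. If a composite were made primary instead, power at 100 per arm would fall from 90% to about 87% (baseline scoring) or 76% (scoring at 35) under the assumptions in step 4, so the sample size and the margin's justification would need rechecking.

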7.5.5.10. Re-intervention Status (Additional surgical procedures)

Participants will be asked whether they have required any type of surgical re-intervention (and if so details of what intervention has been received) for their urological symptoms since receiving their trial intervention.

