	To compare the use of and duration of catheterisation perioperatively and post-intervention	Perioperative and post-intervention catheterisation duration and subsequent use of catheters up to three years post-intervention
	To compare the hospital attendance rate post-intervention	Number and rate of hospital attendances (in patient or outpatient visits) for events/conditions possibly associated with BPE, condition progression, intervention, (including routine follow-up appointments post-intervention) or treatment failure up to 12 months post-intervention
	To compare the blood transfusion rate post-intervention	Number of patients requiring blood transfusions up to six weeks post-intervention
	To compare the incidence of acute urinary retention post-intervention	Number of patients experiencing post- intervention acute urinary retention up to 12 months post-intervention
	To compare the surgical re-intervention rate	Number of patients requiring surgical re-intervention of any type for their urinary symptoms up to 3 years post-intervention
Secondary Economic	To estimate and compare costs and quality of life following intervention over 12 months	Average healthcare costs per participant over 12 months post-intervention for each area of resource use
		Utility scores derived from responses to the EQ-5D-5L questionnaire at baseline, six weeks post-intervention, six months and 12 months post-intervention
		Average QALYs per participant at 12 months post-intervention

	To compare the cost effectiveness of the interventions at two years and three years post-intervention	Incremental cost per quality-adjusted life year (QALY) gained at two and three years post-intervention Cost- effectiveness acceptability curves to assess the probability of each of the interventions being considered cost-effective at different WTP thresholds for a gained QALY at two and three years post-intervention
	To model costs and quality of life over a patient's lifetime	Average healthcare costs per participant over their lifetime
	To model the incremental cost per QALY over the patient's lifetime	ICERs and CEACs derived by extrapolating costs and QALYs from the data observed during the trial
	To estimate the net benefit value of the interventions for each individual	Participants' willingness to pay for each intervention or combination of interventions Incremental net benefit of interventions

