7.1.2. Consent

Potentially eligible participants will be invited for a research specific screening visit where informed consent will be taken. Potential participants will have sufficient time to review the trial documentation prior to this screening visit this will likely be 24 hours but may be less depending on patient driven requests and circumstances, e.g. the patient living a distance away from the hospital and not wishing to return for a separate visit to consent to the study. Patients will be encouraged to ask questions about the trial and consider whether they wish to participate. Patients should be willing to have at least two of the four possible procedures.

The patient will be informed of their right to withdraw from the trial at any time without being subject to any resulting detriment, by revoking his informed consent. Consent discussions will be documented in the participant's medical records.

Written informed consent for the trial will be taken by a delegated member of the research team, (in agreement with local site policies) who is appropriately trained and delegated to do so. All consenting staff will be required to complete the study specific training which will include a section on trial consent and the importance of delivering information about the various study arms with equipoise, in order to avoid inadvertently biasing potential patients. Consent will be obtained prior to any activities undertaken as part of the screening visit (Visit 1).

The original signed consent form will be retained in the Investigator Site File (ISF), with a copy provided to the patient and a copy filed or scanned into the patient's medical notes (depending on local hospital records/patient notes). Participants will specifically consent to their GP and care team (and referring PIC where applicable), being informed of their participation in the trial and for long term follow up by notes review.

In the case of protocol amendments or information becoming available which may affect the participant's willingness to continue in the trial, it may be necessary to re-consent the participant on an updated consent form (after necessary approvals are obtained).

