7.5.5.12. Catheterisation Questionnaire

Information on catheterisation use after the 12 months post-intervention visit will be collected using a catheterisation questionnaire administered at the two and three years post-intervention. Participants will be asked to confirm if they have had a catheter at any point since their last trial visit and if so, to provide the insertion and removal dates (if possible), along with the reason for each episode of catheterisation.

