7.13.1. Withdrawal Criteria

Participants have the right to withdraw from the trial at any time without having to give a reason. The investigator should complete an investigator led withdrawal form on behalf of the participant. If available, the reason for withdrawal should be documented on the paper withdrawal form, the trial database eCRF and the participant's medical notes. Participants who withdraw from the trial will not be replaced.

If a trial participant withdraws from the trial, all data collected up to the point of withdrawal will be retained and included in the analysis. Routine NHS data will also be collected for the trial up to the three year visit timepoint, unless a participant asks for this to stop. Consent for this will be sought on the withdrawal form. A list of possible routine data to be collected is described in the Operative, Perioperative and Post-Operative Parameters section 7.8

Discontinuation from an aspect(s) of the study (as per section 7.14.2.) is preferable to a withdrawal however, in situations where this is not appropriate or feasible, the Investigator can decide to withdraw the participant entirely. Reasons for an Investigator led withdrawal can include an adverse event that renders the participant unable to continue in any aspect of the trial, or where the participant is unable to comply significantly with trial requirements. Advice from the Chief Investigator should be sought where needed.

When an investigator withdraws a participant from the trial they should also complete an investigator led withdrawal form. The participant must be informed of the investigator decision and their return to their routine care pathway in the NHS.

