10.2. Sample Size Calculations

The primary outcome is the change in I-PSS total score between baseline and 12 months. The trial is powered to test the non-inferiority (NI) of each experimental arm to the TURP arm in terms of I-PSS. The three null hypotheses to be tested are:

- The mean difference in 12-month I-PSS total score (adjusted for baseline) between PUL and TURP is > 3
- ii. The mean difference in 12-month I-PSS total score (adjusted for baseline) between Rezum and TURP is > 3
- iii. The mean difference in 12-month I-PSS total score (adjusted for baseline) between iTIND and TURP is > 3

To test each hypothesis, participants will be pooled across the following randomisation schemes:

i. TURP vs PUL ii. TURP vs Rezum		iii. TURP vs iTIND
TURP: PUL: Rezum: iTIND	TURP: PUL: Rezum: iTIND	TURP: PUL: Rezum: iTIND
TURP: PUL: Rezum	TURP: PUL: Rezum	TURP: PUL: iTIND
TURP: PUL: iTIND	TURP: Rezum: iTIND	TURP: Rezum: iTIND
TURP: PUL	TURP: Rezum	TURP: iTIND

In data from the UNBLOCS trial (NIHR HTA 12-35-15) [33] the standard deviation (SD) of the I-PSS score at 12-months follow-up was 6.3 (based on the non-catheterised participants with complete data).

A non-inferiority margin of three points is used. This represents the minimally clinically important difference (MCID) for the outcome. [4,46,47] The non-inferiority hypothesis is equivalent to ruling out TURP providing an improvement of the MCID or greater against a minimally invasive treatment.

Assuming a minimally invasive arm has the same mean I-PSS as TURP, standard non-inferiority sample size formula suggests we would require 12-month information on 100 participants per intervention for each comparison for 90% power to conclude non-inferiority at a one-sided type I error rate of 0.0195 (nQuery). This p-value threshold yields a maximum chance of falsely concluding non-inferiority of 5% assuming a Dunnett correction.

We have inflated this sample size to account for a 25% attrition rate, which was seen in UNBLOCS for patient-reported outcomes. This gives a sample size of 134 participants per intervention for each comparison. Since we are adjusting for baseline I-PSS, we would expect power to be higher than 90%.

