The proportion of participants requiring a readmission, experiencing acute urinary retention, requiring a catheter, or re-intervention during follow-up will be analysed using mixed-effects logistic regression models, including site as a random effect and treatment group and randomisation scheme as fixed effects. Time to readmission, catheterisation, acute urinary retention or re-intervention may also be analysed using a Cox proportional hazards model, depending on the number of events observed. Where there are multiple incidences of these outcomes per participant, the data may also be analysed using suitable models for count data, as appropriate for the distribution of the data. Further details will be provided in the statistical analysis plan.

Safety outcomes, including early post-operative symptoms and post-surgical complications will be analysed in the safety population according to the intervention received. Complications will be tabulated by type and severity, with the number and proportion of participants affected and the total number of occurrences reported.

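### After 12 months, re-intervention and catheter use have no source but a returned questionnaire for men still in the trial, although notes review is consented to and routine data are planned for men who withdraw

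*Protocol*

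**What the plan says.** Protocol section 3 lists two secondary outcomes with a three-year horizon: "Number of patients requiring surgical re-intervention of any type for their urinary symptoms up to 3 years post-intervention" and "subsequent use of catheters up to three years post-intervention".

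Up to the 12-month visit, Protocol 7.7 has the research team collect catheter use, urinary retention and re-intervention at two calls and one on-site visit, with the medical notes consulted where needed. After that, the schedule of events (7.12) holds only remote questionnaires at two and three years. For re-intervention (7.5.5.10), "Participants will be asked whether they have required any type of surgical re-intervention". Catheter use after 12 months is "collected using a catheterisation questionnaire administered at the two and three years post-intervention" (7.5.5.12). The diary in 7.3 is the participant's own memory aid, not a separate source.

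Two other provisions bear on this. Under 7.1.2 every participant consents to his care team being informed and "for long term follow up by notes review". Under 7.13.1, for a man who withdraws, "Routine NHS data will also be collected for the trial up to the three year visit timepoint", unless he asks for this to stop. That section refers by name to the Operative, Perioperative and Post-operative Parameters section for the items, and that section includes catheterisation and surgical re-intervention.

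The analysis (10.3.2) is of proportions: participants "requiring a catheter, or re-intervention during follow-up will be analysed using mixed-effects logistic regression models".

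**The concern.** Both outcomes are events that normally leave a hospital record, so they need not depend on a reply. As written, the protocol arranges to look them up for a man who formally leaves the trial, but not for a man who stays and falls silent. The consent that would allow this is already in hand, and no procedure uses it after 12 months.

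The gap is in data collection. If the late events of silent men are never recorded, no later analysis choice can recover them. The retreatment rates cited in section 2 are low, so the men with unknown late status may well outnumber the events observed. The patient representatives also named the need for future treatments as a concern, which is what the re-intervention outcome measures.

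**Working it through.** **1. The protocol's own planning figure.** Inputs from 10.2: SD 6.3, margin 3, one-sided alpha 0.0195, power 90%, attrition 25%.

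- n per arm = 2(z₀.₉₈₀₅ + z₀.₉₀)² × 6.3² / 3² = 2 × (2.064 + 1.282)² × 39.69 / 9 ≈ 98.7, so 99 by the normal approximation. The noncentral t gives 100 (power 90.06%).
- 100 / 0.75 = 133.3, so 134 per arm; 4 × 134 = 536.

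The stated figures reproduce. The planned loss is 134 − 100 = 34 men per arm. It rests on "We have inflated this sample size to account for a 25% attrition rate, which was seen in UNBLOCS for patient-reported outcomes" and serves the 12-month I-PSS comparison.

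**2. Men without a complete three-year status.** The protocol gives no return rate for years two and three, so a range is shown.

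| Assumed loss | Men per arm (of 134) | Total (of 536) |
|---|---|---|
| 15% | 20 | 80 |
| 25% | 34 | 136 |
| 35% | 47 | 188 |

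**3. Set against the expected events.** Section 2 cites retreatment of 4.4% for Rezum (four years), 2.5% to 9% for PUL and 6.2% for iTIND (two years). The horizons differ, so these are only a guide. At 6.2%, 100 responders give 6.2 events. With 34 unknown, the arm's proportion is bounded by

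- lowest: 6.2 / 134 = 4.6% (no event in any silent man);
- highest: (6.2 + 34) / 134 = 30.0% (an event in every silent man).

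These are extreme limits, not estimates.

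**4. Precision.** SE of a difference between two arms, both at 6.2%: √(2 × 0.062 × 0.938 / n).

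- n = 100: 3.41 points.
- n = 134: 2.95 points, about 14% smaller.

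**5. Bias under an assumed doubled event rate in non-responders (25% loss, both arms alike).** True rate = 0.75r + 0.25 × 2r = 1.25r. For responders at 9% v 4.5%:

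- true: 11.25% v 5.625%, difference 5.6 points, odds ratio (0.1125/0.8875) / (0.05625/0.94375) = 2.13;
- responders only: 9% v 4.5%, difference 4.5 points, odds ratio (0.09/0.91) / (0.045/0.955) = 2.10.

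The risk difference shrinks by a fifth; the odds ratio hardly moves. This calculation also treats silent men as contributing nothing over all three years. Their first-year events are collected by staff, so it probably overstates the shortfall. In this scenario full ascertainment also raises the rates, and the SE of the difference goes only from 3.5 points (100 per arm, 9% v 4.5%) to 3.4 (134 per arm, 11.25% v 5.625%).

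**The case against.** The strongest reply is that little is lost. Events to 12 months are collected by staff. The re-intervention question covers the whole period since the trial procedure, so a year-three reply recovers a missed year-two form. The catheter question looks back to the last trial visit. Vouchers (7.11) and possible central administration (7.4) are aimed at exactly these two contacts. Withdrawn men are covered by 7.13.1, and some of any 25% loss would be such men. All of this stands: only events after the last contact are lost, and only for men who neither reply nor withdraw.

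A reader might infer that a quarter of the men will have no status at all. The protocol does not support that. The 25% is a 12-month planning figure taken from patient-reported outcomes in an earlier trial.

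A reader might also infer that silent men will be counted as event-free, which would give 6.75% v 3.375% in the example above. Nothing in the protocol says so. How non-return is treated belongs to the statistical analysis plan, to which 10.3.2 defers. That section also allows a Cox model, which can censor at last contact, and 10.3.3 provides for missing-not-at-random analyses if dropout differs substantially between arms. Even that scoring would give an odds ratio of 2.07, close to the true 2.13.

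What does not stand is the suggestion that an analysis plan closes the gap. Censoring and sensitivity analyses describe the uncertainty about late events; they do not supply the events.

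**Conclusion.** The point holds in a limited form. For participants who remain in the trial, the protocol names no source but a returned questionnaire for re-intervention and catheter use after 12 months, and it treats them less completely than men who withdraw. The size is uncertain: 34 of 134 men per arm if the 12-month planning loss carried over to later years, 20 to 47 across 15% to 35%, and fewer to the extent that some of these men formally withdraw.

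A material bias in the comparison with TURP is not shown. It would need a higher event rate among non-responders, which is conjecture, and if that excess were equal across arms the odds ratio from the planned logistic model would barely change. An excess that differed between arms could matter more, but the protocol gives no figure for it. The firmer case is completeness and, at equal rates, an SE about 14% smaller. Section 7.4 also says that some men may be followed for only two years; that is a separate cause of an unknown third year. This is a cheap improvement, not a flaw that threatens the trial's main conclusion.

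**What to change.** In Protocol 7.5.5.10 (re-intervention status), 7.5.5.12 and the schedule of events, extend the routine-data provision of 7.13.1, or the notes review consented to in 7.1.2, to every participant who has not refused and has not returned the two- or three-year questionnaire. Name the items to be extracted: re-intervention and catheterisation status, with dates. Record the source of each entry and the date to which the record was checked.

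The cost is an added data page and modest time for existing site teams, who would check notes only for non-responders at two time points. The main limit is that care may be given at other trusts, including spoke sites and referring centres. Absence from local notes should therefore be recorded as such, with its source, and not taken as proof that no event occurred.
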